#### 3.3.2.5 Time to Resolution of Diarrhea

The time from the start of dosing until the first formed stool (except in cases where liquid or unformed stools recurs) will be evaluated as time to resolution of diarrhea.

# 3.3.2.6 Improvement of Clinical Symptoms

Assess the improvement of clinical symptoms, ie, daily stool count, fecal properties, bloody stool, fever, abdominal pain, nausea, and vomiting.

# 3.3.2.7 Drug Sensitivity of Isolated Strain

Determine the minimum inhibitory concentration (MIC) of OPS-2071 for the isolated/identified *C. difficile* or the strain identified as the causative pathogen of enteric infection.

## 3.3.3 Pharmacokinetics Endpoints

#### 3.3.3.1 Plasma Pharmacokinetics

• Plasma concentration of OPS-2071, Cmax, tmax, Cmax/D

## 3.4 Target Number of Patients

A total of 60 patients with 20 patients (10 patients each in CDI and enteric infection groups) in each dosing group

Enroll 10 patients in each dosing group of the CDI group to assess microbiological outcome. For the enteric infection group, enroll at least five patients in each dosing group to assess microbiological outcome with the sum of *Salmonella*, *Campylobacter*, and pathogenic *E. coli*. If a sufficient number of patients are not available for microbiological assessment after enrollment of 10 patients in each group, enroll more patients.

Patients available for microbiological assessment are those assessed as either "excellent," "good," or "poor" according to Table 3.3-2, which means that patients assessed as "Unknown/indeterminate" will not be included in microbiological assessment.

# 4 Investigational Medicinal Products

# 4.1 Test Product and Comparator

## 4.1.1 Test Product

Code Name	OPS-2071
Generic Name	None
Molecular Formula	C 20 H 15 FN 4 O 3
Content and	A pale yellow film coated tablet containing 25, 50, or 100 mg as OPS-2071
Formulation	
Storage Conditions	To be stored in room temperature

# 4.2 Packaging and Labeling

# 4.2.1 Packaging

Blister pack sheets each containing ten 25, 50, or 100 mg IMP tablets are packaged in a box.

### 4.2.2 Contents of Label

The labels of the package box show the following information requested by regulatory authorities in individual countries: specification that the drug is for use in a clinical trial, code name, protocol number, lot number, expiration date, name and address of the sponsor, and other information as precautions etc.

41

# 5 Trial Population

# 5.1 Target Disease

Bacterial enteritis

#### 5.2 Inclusion Criteria

Patients who meet all of the following criteria will be selected.

- 1. The patient is an Asian male or female of minimum legal age to provide consent (ie, 21 years for Singapore, 19 years for Korea, and 20 years for Japan at time of informed consent).
- 2. The patient provides written informed consent before the clinical trial is initiated.
- 3. The patient has distinctive symptoms and findings of bacterial enteritis (regardless of inpatient or outpatient).
- 4. The patient has bacterial enteritis with one or more of the following causative pathogens either proven or presumed:
  - C. difficile, Salmonella, Campylobacter, pathogenic E. coli, and other bacteria estimated to cause bacterial enteritis (except for typhoid bacillus, Salmonella paratyphi A, enterohemorrhagic E. coli, Shigella, and V. cholerae)
- 5. The patient and his/her partner are willing to take contraceptive measures from initiation of IMPs to 4 weeks after administration of IMPs.

#### CDI group:

- 6. The patient satisfies both the following:
  - ✓ Liquid or unformed stools  $\ge 3$  times/day within 24 hours before the start of IMP administration
  - ✓ A positive clinical laboratory result in one of the following methods to confirm CDI within 48 hours before the start of IMP administration:
    - Toxin A/B assay (positive for either or both toxins A and B)
    - PCR (detection of toxin genes)
    - Colonoscopy (findings of pseudomembranous colitis)

### Enteric infection group:

- 7. The patient satisfies all the following:
  - ✓ Liquid or unformed stools  $\ge 3$  times/day within 24 hours before the start of IMP administration
  - ✓ Any of the following clinical findings of enteric infection within 24 hours before the start of IMP administration.

- Either symptom of abdominal pain, nausea, or vomiting
- ✓ Negative toxin A/B assay or PCR within 48 hours before the start of IMP administration.

#### 5.3 Exclusion Criteria

Patients who fall under any of the following exclusion criteria will be excluded from participation in the trial.

- 1. Intractable vomiting, inability to take oral medication, patients with feeding tubes
- 2. The patient has severe or progressive underlying disease or complication, making it difficult to ensure safety in the study or proper efficacy assessment.
- 3. Complication of chronic bowel diseases such as Crohn's disease, ulcerative colitis, irritable bowel syndrome, or colorectal cancer
- 4. History of stem cell transplantation, organ transplantation, or bone marrow transplantation (within 6 months before the screening examination)
- 5. History of total colectomy
- 6. Suspected viral enteritis
- 7. History of allergic conditions caused by quinolone antibacterials
- 8. The patient has a current diagnosis or history of convulsive disorders, such as convulsion and epilepsy
- 9. The patient has a severe hepatic dysfunction (eg, AST [GOT] or ALT [GPT] ≥ 3 times of the upper limit of normal at the study center, etc)
- 10. The patient has a severe cardiac dysfunction (eg, cardiac arrest, ischemic disease)
- 11. The patient has cardiac arrhythmia or congenital or sporadic long QTc syndrome. Or the patient is treated with a drug reported to prolong QTc interval (eg, amiodarone, sotalol, disopyramide, quinidine, procainamide, terfenadine, astemizole, cisapride, pimozide)
- 12. The patient has a moderate or severe renal dysfunction (eg, serum creatinine level  $\geq 2$  mg/dL or necessity of renal dialysis, etc)
- 13. The patient was treated with UGT1A1 inhibitors (atazanavir) within 2 days before the start of IMP administration.
- 14. Women with confirmed or suspected pregnancy or breast-feeding women

Protocol No. 341-13-002

- 15. The patient was treated with another IMPs within 3 months before the screening examination
- 16. Patients judged to be ineligible by the investigator for any other reasons

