# 3.3.2 Efficacy Endpoints

# 3.3.2.1 Microbiological Outcome

Microbiological outcome will be judged according to the assessment criteria shown in Table 3.3-1 and Table 3.3-2 for the bacterial strain isolated as the causative pathogen based on the data from the microbiological examination. For infection due to multiple causative pathogens, microbiological outcome will be assessed for each individual pathogen.

 Table 3.3-1
 Assessment Table for Microbiological Outcome

	Assessment of				
Baseline	Day 4	End of Treatment	Microbiological Outcome		
+	-	_	Excellent		
+	1				
_	+	_	Good		
+	Not applicable				
+	1				
_	+	,	Poor		
+	_	+			
+	Not applicable				
	Others		Unknown/ indeterminate		

+: culture positive, -: culture negative

Not applicable: Bacterial culture test was not performed. The causative pathogen was not isolated or identified.

Table 3.3-2 Assessment Criteria for Microbiological Outcome

Assessment of Microbiological Outcome	Definition			
Excellent	Pathogen is absent from bacterial culture obtained at Day 4 and at the end of treatment.			
Good	Pathogen is still present in bacterial culture obtained at Day 4, and absent from bacterial culture at the end of treatment.			
Poor	Pathogen is still present in bacterial culture obtained at the end of treatment.			
Unknown/indeterminate	Applicable to none of the above but falls under the cases below for example.     Cultures are not available because of withdrawal from the study or other reasons.			
	Culture was obtained after the use of prohibited concomitant drugs/therapies.			
	Any other circumstance, which makes it impossible to define the microbiological response.			

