## 6.2.1 Prohibited Concomitant Drugs and Therapies

The use of following drugs and therapies will be prohibited during the period from the start day of IMP administration to the end day of the trial for items 1 and 7, from screening to the end day of the trial for the following items 2 through 6, and from the start day of IMP administration to the end day of IMP administration for item 8.

- 1) For enteric infection group only: antibiotic agents/synthetic antibacterial agents (oral, injection, suppository)
- 2) For enteric infection group only: non-steroidal anti-inflammatory/analgesic drugs (oral, injection, suppository)\*
- 3) For enteric infection group only: corticosteroid preparation (oral, injection, suppository)
- 4) For enteric infection group only: immunosuppressant medications (oral, injection, suppository)
- 5) For enteric infection group only: biological preparation (TNF inhibitor)
- 6) Antidiarrheal drugs, drugs to inhibit bowel motility
- 7) Other drugs and therapies to treat CDI and enteric infection (eg, fecal microbiota transplantation)
- 8) UGT1A1 inhibitors (atazanavir)
  - \*: Use for purposes other than treating enteric infection is allowed. (Concomitant use is allowed for treating common cold during the trial period.)

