# 6.2.2 Restricted Concomitant Drugs and Foods

Restricted concomitant drugs and foods among of drugs listed below, concomitant use of drugs listed in 1) in principle are prohibited from the start day of the IMP administration to the day of examination at the end of treatment if the drug is used for a purpose other than treatment of CDI.

Protocol No. 341-13-002

However, in cases that drugs are used to treat an underlying disease at the time of screening and cannot be discontinued even after the start day of the IMP administration due to the necessity for continuous drug treatment, such concomitant use is allowed. Drugs listed in items 2) through 5) are allowed to be administered concomitantly as long as the drugs are used at the time of screening and the dose regimen is not changed during the period from screening until the day of examination at the end of treatment.

Drugs listed in item 6) are allowed to administer concomitantly under the following condition: the drugs are used at the time of screening, and the dose regimen is not changed in the period from screening to the end day of trial for CDI groups, or the period from screening to the end day of IMP administration for enteric infection group. If the food described in item 6) is taken, instruct the patient not to change the daily amount of consumption in the period from screening to the end day of the trial.

- 1) For CDI group only: antibiotic agents/synthetic antibacterial agents (oral, injection, suppository)
- 2) For CDI group only: non-steroidal anti-inflammatory/analgesic drugs (oral, injection, suppository)\*
- 3) For CDI group only: corticosteroid preparation (oral, injection, suppository)
- 4) For CDI group only: immunosuppressant medications (oral, injection, suppository)
- 5) For CDI group only: Biological preparation (TNF inhibitor)
- 6) Probiotics
- \*: Use for purposes other than treating CDI is allowed. (Concomitant use is allowed for treating common cold during the trial period.)

[Rationale for establishing the prohibited and restricted concomitant drugs and therapies]

The above defined prohibited and restricted concomitant drugs and therapies were set considering the possible impact on the proper assessment of the efficacy and safety of IMPs. Topical use is allowed for 1) to 4) of the prohibited concomitant drugs.

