Since OPS-2071 is metabolized by UGT1A1 and UGT1A9, concomitant use of No. 8) in the list of prohibited concomitant drugs may increase the plasma concentration of OPS-2071. To secure safety, concomitant use of inhibitors that may increase plasma concentrations of OPS-2071 is prohibited.

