# 7.3 Measures to Be Taken for Patients Visiting or Planning to Visit Other Hospitals or Departments

At the time of obtaining informed consent, the investigator or subinvestigator will confirm whether or not the patient is receiving treatment at another hospital or department. If the patient is receiving treatment at another hospital or department, the investigator or subinvestigator will inform the attending physician of that hospital or department about the patient's participation in the clinical trial and the IMP being used, with the patient's consent. The investigator or subinvestigator will also obtain and record in source documents and the CRF information on the treatment that the patient is receiving at the other hospital or department (name of disease being treated and information on the type of treatment or measures being implemented) and judge whether or not the patient should participate in the trial.

If a patient visits another hospital or department during the trial period, the investigator or subinvestigator will inform the attending physician of that hospital or department about the patient's participation in the clinical trial and the IMP being used, with the patient's consent. The investigator or subinvestigator will also obtain and record in source documents and the CRF information on the treatment that the patient receives at the other hospital or department (name of disease treated and information on the type of treatment or measures implemented) and judge whether or not the patient should continue to participate in the trial.

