#### 9.2 Criteria and Procedures for Withdrawal of Individual Patients

In any of the events listed below, the investigator or subinvestigator will discontinue IMP administration, perform the tests to be performed at withdrawal stipulated in Section 7.1, Schedule and Procedures of the Trial, and promptly inform the sponsor of the withdrawal (Annex, Emergency Contact). The investigator or subinvestigator will record the date and reason for withdrawal in the source documents and CRF.

If withdrawal is necessitated by problems with safety, such as the occurrence of an AE or aggravation of the underlying disease, the investigator or subinvestigator will promptly take appropriate measures and perform follow-up if necessary (refer to Section 8.4 Follow-up Investigation of Adverse Events).

- 1. If the patient wishes to withdraw
- 2. If it is found after the start of the trial that the patient did not meet all the inclusion criteria or fell under any of the exclusion criteria
- 3. If a drug or therapy from either item 1 or item 7 in the list of prohibited concomitant drugs and therapies is used or judged to be required
- 4. If an AE making continuation of trial participation difficult occurs
- 5. If the female patient is found to be pregnant
- 6. If symptoms of the primary disease exacerbate, and the investigator or subinvestigator judges that it is not appropriate to continue the trial participation
- 7. If it becomes impossible to comply with the protocol for any another reason or if the investigator or subinvestigator judges that it is necessary to discontinue the trial participation for any another reason

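### QTc-prolonging drugs exclude a patient at entry, but no concomitant-drug rule bars starting a non-antibacterial one during the 7 or 10 days of dosing

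*Protocol*

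**What the plan says.** Exclusion 11 (Protocol 5.3, repeated in the synopsis) covers arrhythmia and long QTc syndrome and then adds current medication: "Or the patient is treated with a drug reported to prolong QTc interval". Nine example drugs follow, from amiodarone to pimozide. The clause is in the present tense and has no look-back window.

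Section 6.2.1 lists eight prohibited items. The last is UGT1A1 inhibitors, barred "from the start day of IMP administration to the end day of IMP administration for item 8". The rationale at the end of 6.2.2 explains that item: "To secure safety, concomitant use of inhibitors that may increase plasma concentrations of OPS-2071 is prohibited". Section 6.2.2 lists six restricted items. The first, antibacterials in the CDI group, concerns drugs that "in principle are prohibited from the start day of the IMP administration to the day of examination at the end of treatment" when used for something other than CDI, with an exception for treatment already under way at screening that cannot be stopped.

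Withdrawal criterion 3 in section 9.2 reads "If a drug or therapy from either item 1 or item 7 in the list of prohibited concomitant drugs and therapies is used" or is judged to be required. Criterion 2 covers patients found after the start to have been ineligible. Section 6.2 separately says that a patient who has to be treated with a prohibited drug is withdrawn. For treatment received at another hospital or department, section 7.3 asks the investigator to "judge whether or not the patient should continue to participate in the trial".

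**The concern.** The sponsor judged OPS-2071 together with a QTc-prolonging drug unsuitable on the first day of dosing. Followed as written, the protocol lets the same combination arise on any later dosing day, and it gives the site no explicit instruction to avoid it. Nothing in the text explains why the combination would be acceptable later.

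The point concerns new starts only, since patients already on such a drug are kept out. It is a matter of patient safety and of consistency between eligibility and concomitant-drug rules. No endpoint, analysis or sample size depends on it.

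**Working it through.** The protocol states no figure on this point, so the check compares the rules and then prices the fix.

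**1. The two lists.** The prohibited items are antibacterials, NSAIDs/analgesics, corticosteroids, immunosuppressants and TNF inhibitors (these five for the enteric infection group only), antidiarrheals and motility inhibitors, other treatments for CDI or enteric infection, and UGT1A1 inhibitors. The restricted items are the same first five classes for the CDI group, plus probiotics. Items directed at QTc-prolonging drugs: 0 of 8 and 0 of 6. Examples from exclusion 11 that are named in either list: 0 of 9. A QTc-prolonging drug is caught only if it happens to belong to a listed class, chiefly the antibacterials.

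**2. Which drug-use exclusions continue into dosing.**

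| Exclusion | Subject | Continued as |
|---|---|---|
| 11 | QTc-prolonging drugs | not continued |
| 13 | UGT1A1 inhibitors | prohibited item 8 |
| 15 | another investigational product | not continued |
| 17 | CDI treatment (CDI group) | prohibited item 7 |
| 19 | antibacterials (enteric infection group) | prohibited item 1 |

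Three of five continue and two do not. Exclusion 13 is the closest parallel because it too was set for safety.

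**3. Withdrawal rules.** Criterion 3 names items 1 and 7 only. The withdrawal sentence in 6.2 covers any prohibited drug, but a QTc-prolonging drug is not on that list. Criteria 4 and 7, and section 7.3, leave the decision to the investigator.

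**4. ECG schedule (Table 7-1).** ECGs are taken at screening, Day 4, the end-of-treatment visit (Day 11 for CDI, Day 8 for enteric infection) and withdrawal during dosing. The end-of-treatment visit is the day after the last dose. For a drug started after the Day 4 visit, held on Day 4 itself, the remaining dosing days without a scheduled ECG are 10 − 4 = 6 (CDI) or 7 − 4 = 3 (enteric infection), unless the patient withdraws.

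**5. What limits the stakes.** Section 1.2.1 reports no QT prolongation in anesthetized dogs and infers low proarrhythmic potential. Section 1.2.2 reports one QT event in phase 1, which central measurement did not confirm. Section 6.1 reports no safety concerns up to 1200 mg/day for 7 days. Against the highest possible dose here, that margin is 1200/400 = 3; against 200, 100 and 50 mg/day it is 6, 12 and 24. It comes from healthy men over 7 days, while CDI patients are dosed for 10, and no data on combined use with a QTc-prolonging drug are reported.

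**6. Price of the fix.** Section 11.5 assumes detection of almost 100% in CDI and 50% in enteric infection.

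- Expected evaluable patients per dosing group: 10 × 1.0 = 10 (CDI) and 10 × 0.5 = 5 (enteric infection). Both equal the required numbers, so there is no expected slack.
- Share lost per unevaluable patient: 1/10 = 10% (CDI) or 1/5 = 20% (enteric infection).
- Enrolments to replace one: 1/1.0 = 1 (CDI) or 1/0.5 = 2 (enteric infection).
- If 1 to 2 such events occurred (an assumption), the cost is 1 to 2 CDI or 2 to 4 enteric enrolments.

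**The case against.** The strongest reply is that the protocol is not silent. Exclusions 13, 15, 17 and 19 are worded as past treatment within a window before dosing or screening, whereas exclusion 11 is in the present tense. An investigator could therefore treat a patient who starts such a drug as now falling under exclusion 11 and withdraw the patient under criterion 2. This has some force. But criterion 2 reads equally well as ineligibility discovered late, and it does not forbid starting a drug. Sites could apply it differently, so the ambiguity does not close the gap.

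The ECGs are a genuine safeguard and lower the stakes, but they detect an effect rather than prevent the combination. New antibacterials are indeed covered: fully in the enteric infection group, and in principle in the CDI group.

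It is also fair to say that carrying exclusions forward is not a uniform practice. Exclusion 15, "The patient was treated with another IMPs within 3 months before the screening examination", is not carried forward either. Item 8 also rests on a different mechanism, raised plasma concentrations of OPS-2071. A reader might infer that the protocol breaks a rule it set for itself. With two of five exclusions not continued, the text does not support that; UGT1A1 inhibitors are only the nearest precedent.

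**Conclusion.** The gap is real and small. No prohibited or restricted item bars starting a non-antibacterial QTc-prolonging drug during dosing, and whether criterion 2 does so is unclear. Its practical size cannot be estimated, because the protocol gives no frequency of such use. The conclusion rests on reading exclusion 11 and criterion 2 as entry rules, which is the more natural reading but not the only one.

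Two stronger inferences should be resisted. One is that patients have no protection against the combination. The scheduled ECGs, the duty to judge continued participation when a patient is treated elsewhere, and the discretionary withdrawal criteria all offer some. The other is that criterion 3 must be amended for a ban to work. Section 6.2 already withdraws a patient who has to be treated with any prohibited drug, and item 8 operates without being named in criterion 3.

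This is a cheap improvement of low priority.

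**What to change.** - **Section 6.2.1 and the synopsis list:** add an item 9, drugs reported to prolong the QTc interval (examples as in exclusion 11), prohibited from the start day to the end day of IMP administration, the same window as item 8.
- **Section 9.2, criterion 3:** leave unchanged.
- **Table 3.3-2 and its synopsis copy:** state that use of a non-antibacterial item 9 drug does not by itself make a culture Unknown/indeterminate. That category now includes "Culture was obtained after the use of prohibited concomitant drugs/therapies". Without the added sentence, the new listing could remove a patient from the microbiological per protocol set (11.1.3) for a reason unrelated to microbiology.

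The drafting cost is one list item and one sentence, each with its synopsis copy. Concomitant drugs are already recorded with dates under section 6.2, so no new data are needed. The downside is an occasional IMP discontinuation. Each may cost an evaluable patient, though not always, since the withdrawal examination during dosing includes a culture. A lost patient would be replaced at the enrolment cost worked out above. The number of discontinuations cannot be bounded from the protocol.
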